The committee must have the right to monitor ongoing studies. The researcher must provide monitoring information to the committee, especially information about any serious adverse events. No amendment to the protocol may be made without consideration and approval by the committee. After the end of the study, the researchers must submit a final report to the committee containing a summary of the study's findings and conclusions.

Privacy and Confidentiality

24. Every precaution must be taken to protect the privacy of research subjects and the confidentiality of their personal information.

Informed Consent

25. Participation by individuals capable of giving informed consent as subjects in medical research must be voluntary. Although it

may be appropriate to consult family members or community leaders, no individual capable of giving informed consent may be enrolled in a research study unless he or she freely agrees.

26. In medical research involving human subjects capable of giving informed consent, each potential subject must be adequately informed of the aims, methods, sources of funding, any possible conflicts of interest, institutional affiliations of the researcher, the anticipated benefits and potential risks of the study and the discomfort it may entail, post-study provisions and any other relevant aspects of the study. The potential subject must be informed of the right to refuse to participate in the study or to withdraw consent to participate at any time without reprisal. Special attention should be given to the specific information needs of individual potential subjects as well as to the methods used to deliver the information.

After ensuring that the potential subject has understood the information, the physician or another appropriately qualified individual must then seek the potential subject's freely-given informed consent, preferably in writing. If the consent cannot be expressed in writing, the non-written consent must be formally documented and witnessed.

All medical research subjects should be given the option of being informed about the general outcome and results of the study.

27. When seeking informed consent for participation in a research study the physician must be particularly cautious if the potential subject is in a dependent relationship with the physician or may consent under duress. In such situations the informed consent must be sought by an appropriately qualified individual who is completely independent of this relationship.
28. For a potential research subject who is incapable of giving informed consent, the physician must seek informed consent from the legally authorised representative. These individuals must not be included in a research study that has no likelihood of benefit for them unless it is intended to promote the health of the group represented by the potential subject, the research cannot instead be performed with persons capable of providing informed consent, and the research entails only minimal risk and minimal burden.
29. When a potential research subject who is deemed incapable of giving informed consent is able to give assent to decisions about participation in research, the physician must seek that assent in addition to the consent of the legally authorised representative. The potential subject's dissent should be respected.
30. Research involving subjects who are physically or mentally incapable of giving consent, for example, unconscious patients, may be done only if the physical or mental condition that prevents giving informed consent is a necessary characteristic of the research group. In such circumstances the physician must seek informed consent from the legally authorised representative. If no such representative is available and if the research cannot be delayed, the study may proceed without informed consent pro-

vided that the specific reasons for involving subjects with a condition that renders them unable to give informed consent have been stated in the research protocol and the study has been approved by a research ethics committee. Consent to remain in the research must be obtained as soon as possible from the subject or a legally authorised representative.

31. The physician must fully inform the patient which aspects of their care are related to the research. The refusal of a patient to participate in a study or the patient's decision to withdraw from the study must never adversely affect the patient-physician relationship.
32. For medical research using identifiable human material or data, such as research on material or data contained in biobanks or similar repositories, physicians must seek informed consent for its collection, storage and/or reuse. There may be exceptional situations where consent would be impossible or impracticable to obtain for such research. In such situations the research may be done only after consideration and approval of a research ethics committee.

Use of Placebo

33. The benefits, risks, burdens and effectiveness of a new intervention must be tested against those of the best proven intervention(s), except in the following circumstances:

Where no proven intervention exists, the use of placebo, or no intervention, is acceptable; or

Where for compelling and scientifically sound methodological reasons the use of any intervention less effective than the best proven one, the use of placebo, or no intervention is necessary to determine the efficacy or safety of an intervention

and the patients who receive any intervention less effective than the best proven one, placebo, or no intervention will not be subject to additional risks of serious or irreversible harm as a result of not receiving the best proven intervention.

Extreme care must be taken to avoid abuse of this option.

Post-Trial Provisions

34. In advance of a clinical trial, sponsors, researchers and host country governments should make provisions for post-trial access for all participants who still need an intervention identified as beneficial in the trial. This information must also be disclosed to participants during the informed consent process.

Research Registration and Publication and Dissemination of Results

35. Every research study involving human subjects must be registered in a publicly accessible database before recruitment of the first subject.

36. Researchers, authors, sponsors, editors and publishers all have ethical obligations with regard to the publication and dissemination of the results of research. Researchers have a duty to make publicly available the results of their research on human subjects and are accountable for the completeness and accuracy of their reports. All parties should adhere to accepted guidelines for ethical reporting. Negative and inconclusive as well as positive results must be published or otherwise made publicly available. Sources of funding, institutional affiliations and conflicts of interest must be declared in the publication. Reports of research not in accordance with the principles of this Declaration should not be accepted for publication.

Unproven Interventions in Clinical Practice

37. In the treatment of an individual patient, where proven interventions do not exist or other known interventions have been ineffective, the physician, after seeking expert advice, with informed consent from the patient or a legally authorised representative, may use an unproven intervention if in the physician's judgement it offers hope of saving life, re-establishing health or alleviating suffering. This intervention should subsequently be made the object of research, designed to evaluate its safety and efficacy. In all cases, new information must be recorded and, where appropriate, made publicly available.

ARTICLE INFORMATION

Corresponding Author: World Medical Association, [name]; [contact].

Published Online: October 19, 2013.
doi:10.1001/jama.2013.281053.

Disclaimer: ©2013 World Medical Association, Inc. All Rights Reserved. All intellectual property rights in the Declaration of Helsinki are vested in the World Medical Association. The WMA has granted JAMA exclusive rights to publish the

English-language version of the Declaration through December 31, 2013.

Online-Only Content: Audio podcast is available at www.jama.com.

APPENDIX C. BIOPSY SUB-STUDY OF PROTOCOL 747-302: A PHASE 4, DOUBLE-BLIND, RANDOMIZED, PLACEBO-CONTROLLED, MULTICENTER STUDY EVALUATING THE EFFECT OF OBETICHOLIC ACID ON CLINICAL OUTCOMES IN SUBJECTS WITH PRIMARY BILIARY CHOLANGITIS

The following Protocol Concept is being presented as an Appendix to the current 747-302 Protocol Version 3.1. The final Paired Biopsy Sub-Study Protocol will be provided to participating sites as Addendum 1 to the 747-302 Protocol.

Rationale: The purpose of this sub-study is to assess the effect of OCA versus placebo on the histological severity of disease (fibrosis/cirrhosis) in subjects with PBC. In addition, this sub-study will explore the relationship between histological changes and clinical, laboratory, and non-invasive measures indicative of progression to cirrhosis in patients with PBC.

Population	
Subjects must meet all Inclusion and Exclusion criteria for Protocol 747-302
 
Additional Criteria for the Biopsy Sub-Study are:
 
Inclusions:
 
 • Must provide written informed consent and agree to comply with the requirements of the sub-study protocol 
Exclusions:
 
 • Inability to safely undergo a liver biopsy
Sample Size	
N= approximately 45 subjects
 
Assumes 1-sided test
 
80% power to detect a difference in relative risk of progression to cirrhosis at an alpha of 0.2 when OCA event rate is 0.23 (50% risk reduction)
 
80% power to detect a difference in relative risk of progression to cirrhosis at an alpha of 0.3 when OCA event rate is 0.28 (~45% risk reduction)

Study Design / Duration	
Placebo-controlled, randomized, double-blind
 
Participation open to all sites participating in the 747-302 protocol (expectation is approximately 20 sites globally will participate)
 
Placebo, 5-10 mg OCA
 
After meeting all eligibility requirements for this sub-study, subjects will follow the study procedures as outlined in the main protocol for Study747-302.
 
It is expected that subjects will be followed for a minimum of 6 years as in the main protocol.
 
A baseline biopsy must be performed no later than Day 0 (± 7 days) unless biopsy was obtained no more than 6 months before Day 1.
 
Timing of post-treatment biopsy: If a subject develops evidence of probable progression to cirrhosis as assessed by the indicators listed below, another biopsy will be performed at that time; biopsy reports and available clinical, laboratory, and radiological assessments will be used as a basis for adjudication by the

	
hepatic adjudication committee to assure that all events of progression to cirrhosis meet pre-defined criteria and are consistent across sites.
 
A biopsy will be performed at end of study (EOS) on all subjects who have not already had a biopsy based on evidence of the clinical, laboratory, or radiological indicators of progression during the course of the study.

Primary objectives	
To evaluate the effect of OCA compared to placebo on the histological severity of PBC by assessing the following:
 
 • Progression to cirrhosis • Improvement in fibrosis/cirrhosis
Secondary objectives	
To evaluate the effect of OCA compared to placebo on the histological stage of PBC
 
To demonstrate the relationship between histological changes and clinical, laboratory, and non-invasive measurements indicative of progression to cirrhosis in subjects with PBC including:
 
 • Transient Elastography (TE) • Noninvasive scores of liver fibrosis including Enhanced Liver Fibrosis (ELF) and aspartate aminotransferase (AST) to platelet ratio index (APRI),
Indicators of Progression to Cirrhosis informing the timing of biopsy	
Persistent (i.e. 2 consecutive measurements obtained at least 3 months apart) elevation in Fibroscan® TE >16.9 kPa
 
Presence of any of the following:
 
 • Varices • Ascites • Radiological evidence of cirrhosis (nodular liver or enlargement of portal vein and splenomegaly) • Combined low platelet count (<140,000/mm³) with: 
 • Persistent decrease in serum albumin, or • Elevation in prothrombin time/INR (not due to antithrombotic agent use), or • Elevated total bilirubin >2x ULN
Biopsies	Paired biopsies will be read by a central reader
Adjudication	Adjudication of progression of cirrhosis will be performed by an independent hepatic adjudication committee as per the main protocol. All available documentation of progression including biopsy reports will be made available to the adjudicators.
Statistical Analysis	
For each treatment group, the proportion of subjects with and without biopsy-assessed cirrhosis at the end of study by baseline biopsy-assessed cirrhosis status will be presented in a shift table from Baseline to the end-of-study.
 
For the subset of subjects who were non-cirrhotic at Baseline, Kaplan-Meier (KM) estimates of the time to cirrhosis (as assessed by biopsy) will be summarized and graphed by treatment group.
 
For the subset of subjects who were cirrhotic at Baseline, cumulative incidence estimates of the time to improvement in fibrosis/cirrhosis (as assessed by biopsy) will be summarized and graphed by treatment group.

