^a All subjects will have the chemistry panel retested to ensure subjects have two ALP and bilirubin assessments at least 2 weeks apart to calculate the mean result for both analytes. The mean of all screening ALP and bilirubin assessments will be used to determine eligibility. Samples for hematology and coagulation will not be collected at Screening Visit 2.

^b Post-Titration visits must be performed 1 month (+ 1 week) after any up-titration in dose and/or frequency in subjects following modified dosing due to Child-Pugh B and Child-Pugh C hepatic impairment. In subjects following the standard dosing regimen, the post-titration visit must be performed only after the first up-titration to 10 mg OCA or matching placebo, or after ≥3 months at a decreased dose or frequency.

^c Visits should be based on Day 0 (not on the prior visit) with the exception of the Post-Titration Visit, which is based on the date of titration.

- ^d Medical history at Screening and the yearly physical exam will include an assessment of smoking and alcohol consumption history and current habits for both.
- ^e Presence or absence of cirrhosis should be assessed per [Section 9.7.3](#). Cirrhosis status should be repeated as clinically indicated.
- ^f Mayo Risk Score will be calculated based on central laboratory evaluations, diuretic use data, and peripheral edema assessment data captured in the eCRF.
- ^g Child-Pugh Score will be calculated based on ascites assessment, hepatic encephalopathy grade, and central laboratory evaluations per the Child-Pugh scoring system noted in the eCRF.
- ^h Height will be collected at this visit.
- ⁱ The EQ-5D-5L and FIS Quality of Life questionnaires are validated for use in multiple languages. If a validated translation is not available in the local language required for a specific study subject, the data from that questionnaire will not be collected (See [Section 11.1.2.2](#) and [Section 12.2.6](#)).
- ^j Transient elastography (TE) will be conducted at 6-month intervals at all study sites where the Fibroscan[®] TE device is available. Please refer to [Section 9.7.7](#) for additional information related to the allowed windows at Day 0 for this procedure.
- ^k DEXA will be conducted at 12-month intervals at all study sites where the DEXA device is available. Please refer to [Section 9.7.7](#) for additional information related to the allowed windows at Day 0 for this procedure.

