- ^l Endoscopy will be conducted at selected study sites where the device is available to assess for the presence of oesophageal varix/varices. Please refer to [Section 9.7.7](#) for additional information related to the allowed window at Day 0 for this specific procedure.
- ^m Ultrasound will be conducted to enhance HCC surveillance. For all on study (eg, post-Day 0) ultrasounds: unless HCC has already confirmed by biopsy, a second confirmatory image (eg, MRI) should be obtained to confirm if a study endpoint has been met.
- ⁿ Health Outcome Assessments: Data related to non-study related medical or surgical treatment procedures that the subject underwent and any medically relevant health care provider (HCP) or non-HCP related office visits that the subject attended should be collected throughout the study.
- ^o Pre-titration tolerability assessment, which include a review of AEs and a review of safety laboratory results (eg, chemistry, hematology, and coagulation), must be completed by the Investigator before any up-titration can occur as defined in [Section 7.4.1](#). Lab results obtained within 2 months prior to any up-titration may be used for assessment.
- ^p Dose Titration is based on cirrhosis status ([Section 9.7.3](#)) and Child-Pugh Score ([Section 9.7.4](#)). The initial dose titration of investigational product may occur at the Month 3 visit, or any study visit thereafter for subjects on all dosing regimens, based on tolerability and biochemical response. Subsequent dose titration(s) for subjects who are classified as Child-Pugh B or Child-Pugh C and following a modified dosing schedule may occur no earlier than 6 weeks after the previous dose titration. For complete modified dose titration criteria, refer to [Appendix A](#).
- ^q Subjects will be instructed to begin dosing on the day after the Day 0 visit (ie, on Day 1) and to take investigational product at approximately the same time of day. Subjects must be instructed to swallow the tablet whole; they must not chew, divide, or crush the tablet.
- ^r The subject should be instructed to fast overnight (at least 8 hours) prior to each visit. Fasting is required prior to all study visits (except Screening Visit 1) but water is permitted.

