7.4.1. Pre-Titration Tolerability Assessment Requirements

Tolerability of investigational product must be assessed prior to titrating a subject to a higher dose. A review of adverse events and safety laboratory results (eg, chemistry, hematology, and coagulation) obtained within 2 months of the up-titration visit must be performed as part of the investigational product tolerability assessment, prior to any planned up-titration in study medication (eg, Month 3, Month 6). Safety laboratory results obtained at the Month 1 visit (for titration at Month 3) or at the 1 Month Post-Titration Assessment visit (for titration prior to or at the subsequent quarterly visit) are acceptable for review purposes; however, if for any reason, laboratory results are not available at the time of the planned up-titration visit, additional laboratory samples must be obtained and reviewed, prior to up-titrating the subject to a higher dose.

To be eligible for a dose up-titration:

- Subjects should not be experiencing significant AEs that are suspected to be related to investigational product (eg, severe pruritus) or displaying other symptoms that may indicate intolerability of investigational product.
- There must be no clinically significant increase (as determined by the investigator) in the subject's liver function tests. Subjects whose total bilirubin is $>2\times$ baseline (and $>ULN$) cannot be up-titrated, and additional unscheduled safety visit procedures, outlined in [Section 9.7.19](#), should be implemented, as required.

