9.7.10. Post-Titration Visit Procedures

- Perform a physical examination.
- Assess and record AEs.
- Review and record concomitant medications.
- Assess investigational product compliance, perform investigational product accountability, and review dosing diary with the subject.
- Obtain blood samples for serum chemistry, hematology, and coagulation tests.
- Provide the subject with a dosing diary to document his or her dosing.
- In the event it is not feasible for the subject to return the site for the above referenced procedures, the following alternative visit procedures are available, to help ensure compliance with the Post-Titration laboratory requirements:
 - At the Up-titration Visit, the subject can be provided with the central laboratory collection kit and shipping materials associated with the Post-Titration visit, and have the laboratory specimen collection performed at his or her local doctor's office or designated laboratory collection center. The subject must also be contacted via telephone at the Post-Titration Visit time point to assess AEs, review concomitant medications, and assess investigational product compliance;
 - If all other options for the collection of the Post-Titration laboratory samples have been exhausted, the use of a local laboratory for the Post-Titration samples would be accepted for this visit although any laboratory data obtained from a local laboratory will not be captured in the eCRF or included in the study analysis. A

copy of the local laboratory report would need to be provided to the investigator for review and available in the source records. The subject must also be contacted via telephone at the Post-Titration Visit time point to assess AEs, review concomitant medications, and assess investigational product compliance;

- Schedule the next visit, reiterate dosing instructions, and advise the subject:
 - NOT to take investigational product on the morning of the next visit, and
 - To bring the investigational product bottle(s); s/he will dose at the clinic (if this is in compliance with the established dosing frequency), and
 - To fast overnight (at least 8 hours) prior to the next visit. Fasting is required prior to all study visits, but water is permitted.

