following review of the pre-titration laboratory results to assess safety and tolerability, the dosing frequency of 5 mg OCA or matching placebo should be increased to twice weekly (at least 3 days apart). Subjects who have maintained the twice weekly dosing frequency for a minimum of at least 6 weeks, and meet the dose titration criteria, should up-titrate to twice weekly dosing with 10 mg OCA or matching placebo. Subjects with at least 6 weeks of twice weekly dosing at 10 mg OCA or matching placebo, and meeting dose titration criteria, should up-titrate to the maximum allowed dose of 5 mg OCA or matching placebo once daily.

Investigators may decrease the dosing frequency (back to once or twice weekly) or dose for any subject at any time during the study, as considered clinically appropriate (eg, tolerability).

Modified Dosing Regimen for Subjects with Child-Pugh C Hepatic Impairment

Subjects with cirrhosis and classified as Child-Pugh C at Screening will follow a modified dosing schedule receiving 5 mg OCA or matching placebo once weekly as described in [Figure 2](#). After a minimum of 3 months dosing once weekly with 5 mg OCA or matching placebo, and following review of the pre-titration laboratory results to assess safety and tolerability, the dosing frequency of 5 mg OCA or matching placebo should be increased to twice weekly (at least three days apart). Subjects who have maintained the twice weekly dosing frequency for a minimum of at least 6 weeks, and meet the dose titration criteria, should up-titrate to the maximum allowed dose of 10 mg OCA or matching placebo twice weekly.

Investigators may decrease the dosing frequency (back to once weekly) or dose for any subject at any time during the study, as considered clinically appropriate (eg, tolerability).

Dose Titration due to Change in Cirrhosis or Child-Pugh Score

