Subjects on a modified dosing regimen who demonstrate a change in cirrhosis status and/or Child-Pugh Score should have their dose of investigational product modified to match their current status per the appropriate dosing regimen (see [Section 7.4](#), [Table 5](#)); however, changes to the dosing regimen are not mandatory and should be based on clinical judgment as well as changes in status. Changes in Child-Pugh Score that result from a transient, explainable change in laboratory parameters should be documented appropriately, and should not necessarily result in a change to the dosing regimen. Investigators may contact the Medical Monitor at any time to discuss potential changes to dosing.

Possible scenarios for dosing modifications include:

- Subjects who develop cirrhosis during the course of the trial with a classification of Child-Pugh B or C
- Subjects with pre-existing cirrhosis who demonstrate a change in the Child-Pugh Score from A to B or C at any point in the study
- Improvement in classification of Child-Pugh Score from C to B
- Improvement in classification of Child-Pugh Score from B to A; these subjects may be eligible to transition to the standard dosing regimen

Subjects may titrate dose and dosing frequency up or down as appropriate, within the appropriate dosing regimen. Up-titration should be done per Investigator discretion and be guided by the pre-titration tolerability assessments outlined in [Section 7.4.1](#). A 1-Month Post-Titration

Assessment must be performed any time a subject's dose or frequency is up-titrated (see [Section 7.1.2](#) and [Section 9.7.10](#)).

Unscheduled Titration Visit, Optional Visit

An unscheduled up-titration visit may be scheduled for as early as 6 weeks after the initial titration visit (or subsequent titration visit) occurs for subjects who are following the modified dosing regimen. The visit procedures required for the unscheduled titration visit are outlined below. Subjects who up titrate at an unscheduled visit will continue to follow the regular visit schedule for all other study visits.

For subjects who up titrate at an unscheduled visit the following procedures will be performed:

- Assess and record AEs.
- Review and record concomitant medications.
- Perform the pre-Titration Tolerability Assessment as outlined in [Section 7.4.1](#).
- Assess the subject's supply of investigational product to ensure an adequate amount. Access the IWRS and dispense investigational product if necessary.

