- Provide the subject with a dosing diary to document his or her dosing.
- Schedule the next visit, reiterate dosing instructions, and advise the subject:
 - NOT to take investigational product on the morning of the next visit, and
 - To bring the investigational product bottle(s); s/he will dose at the clinic (if this is in compliance with the established dosing frequency), and
 - To fast overnight (at least 8 hours) prior to the next visit. Fasting is required prior to all study visits, but water is permitted.

For subjects who up titrate at an unscheduled visit: The + 1-week window week related to the 1-Month Post-Titration visit can be extended for up to an additional 5 weeks to allow for the post-titration assessment to be performed during one of the subject's regularly scheduled study visits. If the window is extended past +1 week allowed visit window, at a minimum, a telephone safety contact should then be performed 1-month post-titration.

**APPENDIX B. ETHICAL CONDUCT ACCORDING TO THE
DECLARATION OF HELSINKI FOR COUNTRIES
PARTICIPATING OUTSIDE THE US (DECLARATION
OF HELSINKI, FORTELEZA, BRAZIL, 2013)**

Special Communication

World Medical Association Declaration of Helsinki Ethical Principles for Medical Research Involving Human Subjects

World Medical Association

Adopted by the 18th WMA General Assembly, Helsinki, Finland, June 1964, and amended by the:
 29th WMA General Assembly, Tokyo, Japan, October 1975
 35th WMA General Assembly, Venice, Italy, October 1983
 41st WMA General Assembly, Hong Kong, September 1989
 48th WMA General Assembly, Somerset West, Republic of South Africa, October 1996
 52nd WMA General Assembly, Edinburgh, Scotland, October 2000
 53rd WMA General Assembly, Washington, DC, USA, October 2002 (Note of Clarification added)
 55th WMA General Assembly, Tokyo, Japan, October 2004 (Note of Clarification added)
 59th WMA General Assembly, Seoul, Republic of Korea, October 2008
 64th WMA General Assembly, Fortaleza, Brazil, October 2013

Preamble

1. The World Medical Association (WMA) has developed the Declaration of Helsinki as a statement of ethical principles for medical research involving human subjects, including research on identifiable human material and data.

The Declaration is intended to be read as a whole and each of its constituent paragraphs should be applied with consideration of all other relevant paragraphs.

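### In Version 3.1, a Child-Pugh B subject stepped up to 10 mg twice weekly at an unscheduled visit may go on to 5 mg daily on labs drawn at 5 mg twice weekly

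*Protocol*

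**What the plan says.** All operative text is in protocol Version 3.1.

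- **Default draw.** Section 7.1.2, Table 1, footnote b: "Post-Titration visits must be performed 1 month (+ 1 week) after any up-titration in dose and/or frequency in subjects following modified dosing". Section 9.7.10 includes chemistry, hematology and coagulation samples in that visit.
- **Next step.** For Child-Pugh B, Appendix A makes eligible for 5 mg daily "Subjects with at least 6 weeks of twice weekly dosing at 10 mg OCA or matching placebo" who meet the titration criteria. An unscheduled up-titration visit may be held from six weeks after the previous titration, and its procedure list contains no blood draw.
- **Extension.** After an up-titration at an unscheduled visit, Appendix A says the post-titration window "can be extended for up to an additional 5 weeks to allow for the post-titration assessment to be performed" at a regular visit. If it is used, the minimum at one month is a telephone contact.
- **Labs that may be relied on.** Table 1, footnote o: "Lab results obtained within 2 months prior to any up-titration may be used for assessment". Section 7.4.1 also requires a laboratory review before each up-titration and says that results from the "1 Month Post-Titration Assessment visit (for titration prior to or at the subsequent quarterly visit) are acceptable for review purposes". If results are not available, "additional laboratory samples must be obtained and reviewed, prior to up-titrating the subject to a higher dose".
- **Laboratory conditions.** Section 7.4.1 bars up-titration when total bilirubin exceeds twice baseline (and the ULN). Section 7.4 makes up-titration depend also on ALP and/or bilirubin response.

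**The concern.** The default rule and the six-week minimum fit together: a sample is taken on the current dose before the next step can be taken. The extension breaks that order. It moves the draw past the point at which the next step opens, and nothing in Section 7.4.1 or Appendix A holds that step until the deferred sample has been read. The two-month look-back then lets labs from the previous dose stand in.

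At stake is the laboratory check on subjects with moderate hepatic impairment, for whom the protocol built a slower ladder with extra visits. The bilirubin bar and the biochemical-response criterion could both be applied to values that say nothing about the dose being exceeded.

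**Working it through.** The document states no figure to reproduce; this is a check of visit windows. Assumptions: 1 month = 30 days, 2 months = 61 days, nominal Month 3 = day 91, nominal Month 6 = day 182. T1, T2 and T3 are Titrations 1 to 3 in Section 7.3, Table 3.

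**Default order.** Draw at 30 to 30 + 7 = 37 days after a step. Next step from 6 × 7 = 42 days. The draw precedes the earliest next step by 42 − 37 = 5 to 42 − 30 = 12 days.

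**With the extension.** Latest draw = 30 + 7 + 35 = 72 days after the step, which is 72 − 42 = 30 days after the next step opens.

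**Which step is affected.** The extension concerns steps at unscheduled visits, which come after the initial titration, so T2 is the first it can reach. Child-Pugh C stops at T2. On the planned ladder only Child-Pugh B, T2 to T3, is exposed.

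**Schedule with T1 at Month 3.**

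| Event | Calculation | Day |
|---|---|---|
| T1, to 5 mg twice weekly | Month 3 | 91 |
| Post-T1 labs | 91 + 30 to 91 + 37 | 121–128 |
| T2 (unscheduled), to 10 mg twice weekly, earliest | 91 + 42 | 133 |
| T2, latest with those labs still valid at T3 | 121 + 61 − 42 to 128 + 61 − 42 | 140–147 |
| T3, to 5 mg daily | 133 + 42 to 147 + 42 | 175–189 |
| Month 6 visit window | 182 ± 14 | 168–196 |
| Extension limit for T2 on day 133 | 133 + 72 | 205 |

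The post-T1 labs are 175 − 128 = 47 to 61 days old at T3. The Month 6 window (168–196) overlaps the T3 range (175–189), so the draw can come before T3, on the same day, or up to 196 − 175 = 21 days after it.

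**A plain example.** T2 on day 133 and T3 at the nominal Month 6 visit on day 182. The post-T1 labs are 182 − 128 = 54 to 182 − 121 = 61 days old, still inside the look-back. The Month 6 draw is 182 − 133 = 49 days after T2: past the default limit of 37, within the extended limit of 72. That sample is taken on 10 mg twice weekly, but its result need not be known when the dose is raised.

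**Calendar check.** Real calendar months were used over 365 Day 0 dates and 8 draw offsets (365 × 8 = 2,920), with T2 and T3 at their six-week minimums. The path was open in 2,920 of 2,920 schedules, with labs 46 to 56 days old at T3. With T3 at the nominal Month 6 date, the labs were still valid in 2,916 of 2,920. Without the extension, the default window ran past T3 in 0 of 2,920. These counts show what the wording allows at those intervals and that the extension is the cause. They are not frequencies.

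**Dose.** 5 × 2 = 10 mg per week when the labs are drawn, 10 × 2 = 20 after T2, 5 × 7 = 35 after T3: 35 / 10 = 3.5-fold across two steps on one lab set.

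**The case against.** The strongest reply is that the rules, read together, already imply the right order. Appendix A says a post-titration assessment must follow every up-titration. Section 7.4.1 pairs each titration with labs from the preceding step and calls for new samples when results are not available. Section 7.4 makes escalation depend on biochemical response, which labs predating the dose cannot show. The intent is fair to infer, but none of these provisions fixes a draw date or a dose. Labs under two months old are available in the ordinary sense, and Section 7.4.1 expressly accepts post-titration labs for a titration before or at the next quarterly visit.

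Several stronger readings are tempting, and the document does not support them:

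- *That no sample is ever taken on 10 mg twice weekly.* The Month 6 draw can precede T3 or fall on the same day.
- *That two steps pass on one laboratory review.* Section 7.4.1 requires a review before each, so it is one lab set reviewed twice.
- *That the same gap opens freely after Month 6.* With Month 6 labs on day 182, T2 can be no later than 182 + 61 − 42 = day 201, and a nominal Month 9 visit (day 273) lies within the 72-day limit only if T2 is on that last day (201 + 72 = 273). Any earlier T2 needs an early Month 9 visit.
- *That subjects are harmed or left unwatched.* Adverse-event review and the telephone contact remain, the dose can be reduced at any time (Section 7.4), and Section 8.4.3.1 requires repeat testing when bilirubin exceeds twice baseline. Section 5.5.2.2 predicts 8.0-fold plasma but only 1.5-fold liver exposure in Child-Pugh B and reports no apparent safety impact. Section 7.4, Table 5, lets a subject newly in Child-Pugh B stay on 5 mg daily.
- *That the gap is in the latest protocol.* Version 4 (10 May 2017) lists Section 7.4.1 and Appendix A under the same titles and adds liver-chemistry monitoring and interruption sections, but the text of these sections is not shown.

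**Conclusion.** The point holds for Version 3.1 as a permission in the wording, not a requirement. A Child-Pugh B subject whose T2 is unscheduled may go from 20 to 35 mg per week with the bilirubin bar and the biochemical-response criterion applied to labs 47 to 61 days old, drawn at 10 mg per week. The deferred draw falls anywhere from before T3 to 21 days after it. This rests on T1 at Month 3, T2 at or near its six-week minimum (day 133 to 147), and a plain reading of the rule on unavailable results. How often it would happen and how many Child-Pugh B subjects there are cannot be known from the document; no harm is shown. It is a cheap safety improvement, not an error in the analysis.

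**What to change.** Add one sentence to Section 7.4.1 and one to Appendix A:

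- for subjects on the modified regimen, labs reviewed before any up-titration must have been drawn on the dose being escalated from;
- if the post-titration draw is deferred under the five-week extension, the next up-titration waits until that result has been reviewed.

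Check whether Version 4 kept the wording of these two places and, if so, make the change there.

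The cost for an affected subject is one of two things. Either the draw is taken when footnote b already places it (day 133 + 30 = 163 to 133 + 37 = 170 for T2 on day 133) instead of being merged with Month 6, or T3 waits up to about 3 weeks plus laboratory turnaround. The separate draw need not mean a site visit: under Section 9.7.10 "the subject can be provided with the central laboratory collection kit and shipping materials associated with the Post-Titration visit" and have the sample taken locally.
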